5.3 RANDOMIZATION

The eligible subjects assigned to each of the three cohorts will be asked to come to the clinic for their scheduled day 0 visit. After a history and physical exam is performed to ensure

that they are eligible for participation in the study, blood will be collected for the studies outlined in Section 5.21. Study participants will be assigned a unique study number.

Randomization to either the AMA1-C1/Alhydrogel[®] + CPG 7909 vaccine or 80 µg AMA1-C1/Alhydrogel[®] vaccine will be done online using the enrollment module of the Internet Data Entry System (IDES). The randomization codes will be included in the enrollment module for the trial. Each subject enrolled into the trial is assigned a treatment code after demographic and eligibility data have been entered into the system. The site will be provided with a code list to be kept in a secure place.

5.4 IMMUNIZATION PROCEDURE:

Subjects will receive three immunizations, on Days 0, 28, and 56. 0.50 mL of AMA1-C1/Alhydrogel[®] or 0.55 mL of AMA1-C1/Alhydrogel[®] + CPG 7909 will be delivered by IM in the deltoid muscle with a 22-gauge needle of appropriate length after preparation of the site with alcohol. Successive vaccinations will be given in alternating arms.

5.5 STUDY DAY 0 (DAY OF FIRST VACCINATION)

1. Verify that Informed Consent was obtained.
2. Verify that all applicable eligibility criteria have been met.
3. Perform abbreviated history and physical exam, focusing the history and physical exam on any acute complaints.
4. Obtain blood for hematology, biochemistry, rheumatoid factor, anti-dsDNA, ANA, C3, C4, CH50, anti-AMA-1 antibody ELISA, B and T cell analysis, and *P. falciparum* growth inhibition assay (GIA).
5. Obtain urine for urine dipstick testing.
6. For females, obtain a urine sample for β-hCG testing. Ensure that test is negative before proceeding; a positive test will exclude the volunteer from the trial.
7. Record vital signs (blood pressure, temperature, heart rate and respiratory rate).
8. Administer the vaccine.
9. Observe for 30 minutes after vaccination to evaluate for immediate adverse reactions.
10. Give subject oral thermometer, diary card and instructions for completion.

5.6 STUDY DAY 3

1. Perform interim history and physical exam (abbreviated H&P to include: injection site, skin, lymph nodes, and other body systems felt to be necessary by examining clinician), emphasizing examination of any acute complaints.
2. Record vital signs.
3. Obtain blood for hematology and biochemistry tests, and B and T cell analysis.
4. Review diary card.

5.7 STUDY DAY 7 +/- 1

1. Perform interim history and examination of the injection site, and physical exam if indicated by acute complaints.
2. Record vital signs.
3. Obtain blood for hematology, rheumatoid factor, anti-dsDNA, ANA, and B and T cell analysis.
4. Collect Day 0-6 diary card.

5.8 STUDY DAY 14 +/- 2

1. Perform interim history and examination of the injection site, and physical exam if indicated by acute complaints.
2. Record vital signs.
3. Obtain blood for hematology, biochemistry, and anti-AMA-1 antibody ELISA.
4. Obtain urine for urine dipstick testing.

5.9 STUDY DAY 28 +/- 4 (DAY OF SECOND VACCINATION)

1. Perform interim history and physical exam, emphasizing examination of any acute complaints.
2. Obtain blood for hematology, biochemistry, rheumatoid factor, anti-dsDNA, ANA, anti-AMA-1 antibody ELISA, and B and T cell analysis.
3. Obtain urine for urine dipstick testing.
4. For females, obtain a urine sample for β -hCG testing. Ensure that test is negative before proceeding; a positive test will exclude the volunteer from receiving further vaccinations.
5. Record vital signs.
6. Administer the vaccine.

7. Observe for 30 minutes after vaccination to evaluate for immediate adverse reactions.
8. Give subject oral thermometer, diary card and instructions for completion

5.10 STUDY DAY 31 (3 DAYS AFTER SECOND VACCINATION)

1. Perform abbreviated history and physical exam (abbreviated H&P to include: injection site, skin, lymph nodes, and other body systems felt to be necessary by examining clinician), emphasizing examination of any acute complaints.
2. Record vital signs.
3. Obtain blood for hematology and biochemistry tests, and B and T cell analysis.
4. Review diary card,

5.11 STUDY DAY 35 +/- 1 (7 DAYS AFTER SECOND VACCINATION)

1. Perform interim history and examination of the injection site, and physical exam if indicated by acute complaints.
2. Record vital signs.
3. Obtain blood for hematology and B and T cell analysis, and rheumatoid factor, anti-dsDNA, and ANA.
4. Collect Day 0-6 diary card.

5.12 STUDY DAY 42 +/- 2 (14 DAYS AFTER SECOND VACCINATION)

1. Perform interim history and examination of the injection site, and physical exam if indicated by acute complaints.
2. Record vital signs.
3. Obtain blood for hematology, biochemistry, anti-AMA-1 antibody ELISA, and GIA.
4. Obtain urine for urine dipstick testing

5.13 STUDY DAY 56 +/- 4 (DAY OF THIRD VACCINATION)

1. Perform interim history and physical exam, emphasizing examination of any acute complaints.
2. Obtain blood for hematology, biochemistry, rheumatoid factor, anti-dsDNA, ANA, anti-AMA-1 antibody ELISA, GIA and B and T cell analysis.
3. Obtain urine for urine dipstick testing.

4. For females, obtain a urine sample for β -hCG testing. Ensure that test is negative before proceeding; a positive test will exclude the volunteer from receiving further vaccinations.
5. Record vital signs
6. Administer the vaccine.
7. Observe for 30 minutes after vaccination to evaluate for immediate adverse reactions.
8. Give subject oral thermometer, diary card and instructions for completion

5.14 STUDY DAY 59 (3 DAYS AFTER THIRD VACCINATION)

1. Perform abbreviated history and physical exam (abbreviated H&P to include: injection site, skin, lymph nodes, and other body systems felt to be necessary by examining clinician), emphasizing examination of any acute complaints.
2. Record vital signs.
3. Obtain blood for hematology and biochemistry tests, and B and T cell analysis.
4. Review diary card.

5.15 STUDY DAY 63 +/- 1 (7 DAYS AFTER THIRD VACCINATION)

1. Perform interim history and examination of the injection site, and physical exam if indicated by acute complaints.
2. Record vital signs.
3. Obtain approximately blood for hematology, rheumatoid factor, anti-dsDNA, ANA, and B and T cell analysis.
4. Collect Day 0-6 diary card.

5.16 STUDY DAY 70 +/- 2 (14 DAYS AFTER THIRD VACCINATION)

1. Perform interim history and examination of the injection site, and physical exam if indicated by acute complaints.
2. Record vital signs.
3. Obtain blood for hematology, biochemistry, anti-AMA-1 antibody ELISA, and GIA.
4. Obtain urine for urine dipstick testing.

5.17 STUDY DAY 84 +/- 14 (28 DAYS AFTER THIRD VACCINATION)

1. Perform interim history and examination of the injection site, and physical exam if indicated by acute complaints.
2. Obtain blood for hematology, rheumatoid factor, anti-dsDNA, ANA, B and T cell analysis, anti-AMA-1 antibody ELISA.
3. Obtain urine for urine dipstick testing.

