2.2 SECONDARY OBJECTIVES

- 2.2.1 To demonstrate that the addition of CPG 7909 improves the immune responses to AMA1-FVO and AMA1-3D7, as compared to AMA1-C1/Alhydrogel[®] at day 70 (14 days after 3rd vaccination).
- 2.2.2 To determine the dose of AMA1-C1/Alhydrogel[®] + CPG 7909 that generates the highest serum antibody levels of AMA1-FVO and AMA1-3D7 at day 70.
- 2.2.3 To assess and compare the duration of antibody responses to AMA1-FVO and AMA1-3D7 proteins by enzyme-linked immunosorbent assay (ELISA) over an 8 month period (6 months after 3rd vaccination).
- 2.2.4 To perform exploratory studies of B and T cell populations both before and after vaccination.

2.3 TERTIARY OBJECTIVES:

The following objectives are for informational purposes only:

- 2.3.1 To measure the biological activity of the antisera by an in vitro parasite growth inhibition assay using FVO and 3D7 parasites.
- 2.3.2 To determine the relationship between anti-AMA1 antibody concentration as determined by ELISA and the degree of in vitro growth inhibition of *P. falciparum*.
- 2.3.3 To determine the relative specificity of the antibodies to a range of AMA1 serotypes in addition to FVO and 3D7, as judged by ELISA and growth inhibition on a select panel of parasites with typed AMA1 antigens.

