5.18 STUDY DAY 140 +/- 14 (84 DAYS AFTER THIRD VACCINATION)

1. Perform interim history and perform physical exam if indicated by complaints or history.
2. Obtain blood for hematology, B and T cell analysis, anti-AMA-1 antibody ELISA.

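### The Day 84 window (± 14 days) overlaps the Day 70 window on Days 70-72, so the sample labelled 28 days after dose 3 can be taken at the 14-day time point: a minor defect that is cheap to fix

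*Protocol*

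**What the plan says.** The third dose is given at the visit headed "STUDY DAY 56 +/- 4 (DAY OF THIRD VACCINATION" (Protocol 5.13). Two of the later visits are "STUDY DAY 70 +/- 2 (14 DAYS AFTER THIRD VACCINATION" (5.16) and "STUDY DAY 84 +/- 14 (28 DAYS AFTER THIRD VACCINATION" (5.17). The contents list repeats both windows, so the ± 14 is not a slip in one place.

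Both visits draw an antibody ELISA. At Day 70 the instruction is "Obtain blood for hematology, biochemistry, anti-AMA-1 antibody ELISA, and GIA"; at Day 84 it is "Obtain blood for hematology, rheumatoid factor, anti-dsDNA, ANA, B and T cell analysis, anti-AMA-1 antibody ELISA". The flow sheet (5.22) lists the visits in that order, as V12 and V13. The protocol gives no minimum interval between them and no rule for a sample that lies in both windows.

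The Day 84 ELISA serves the secondary objective "To assess and compare the duration of antibody responses to AMA1-FVO and AMA1-3D7 proteins" over eight months (2.2.3). Section 9.3 plans to meet it by describing responses over time by dose, by describing individual responses, and by longitudinal models. The primary immunogenicity endpoint is the Day 70 ELISA (9.2.2).

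**The concern.** A half-width of 14 days equals the whole nominal interval between the two visits, so the window does not hold the visit to its own label. A subject seen on Day 70, 71 or 72 can satisfy both visits, while another subject's Day 84 sample may be taken four weeks later.

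Two uses of the data depend on the label meaning roughly the same time in every subject:

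- **By-visit descriptions at Day 84.** A summary of ELISA or B and T cell results would pool samples from 14 to 42 nominal days after dose 3. The samples four weeks after doses 1 and 2 are taken at visits with ± 4 ("STUDY DAY 28 +/- 4 (DAY OF SECOND VACCINATION" and Day 56), so the three would not be like for like.
- **Autoantibodies.** After dose 3, rheumatoid factor, anti-dsDNA and ANA are scheduled only on Days 63, 84 and 236. Section 1.2.4 describes one CPG 7909 recipient whose anti-dsDNA rise was detected two weeks after the second and third doses and had returned to normal before the third. If such a signal is transient, a sample at 14 days and one at 42 days do not give the same chance of seeing it.

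**Working it through.** **Inputs (Protocol).** Dose 3: Day 56 (5.13). Visits: Day 70 ± 2 (5.16), Day 84 ± 14 (5.17), Day 140 ± 14 (5.18), Day 236 ± 30 (5.19).

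**1. The plan's own labels.** 70 - 56 = 14, 84 - 56 = 28, 140 - 56 = 84 and 236 - 56 = 180 days after dose 3. All four headings are reproduced.

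**2. Windows.** Day 70: 70 - 2 = 68 to 70 + 2 = 72. Day 84: 84 - 14 = 70 to 84 + 14 = 98. Shared days: 70, 71, 72. In nominal days after dose 3, the Day 84 visit covers 70 - 56 = 14 to 98 - 56 = 42. If the windows run from the actual third dose instead, the ranges are 12-16 and 14-42 days and still overlap. Among all consecutive visits with a stated window, this is the only overlap.

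**3. Gap between the two samples.** Shortest 70 - 72 = -2 days; longest 98 - 68 = 30 days; nominal 14. There are 5 × 29 = 145 permitted day pairs: 3 (2.1%) fall on the same day, 3 (2.1%) are reversed, and 35 (24%) are less than 7 days apart or reversed. These are counts of what the text permits, not forecasts of how visits will be booked.

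**4. Effect on a comparison by nominal visit.** The protocol gives no antibody half-life, so 20 to 60 days is assumed. The ratio of Day 84 to Day 70 is 2^(-gap/half-life):

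| Half-life (days) | gap -2 | gap 14 | gap 30 |
|---|---|---|---|
| 20 | 1.07 | 0.62 | 0.35 |
| 40 | 1.04 | 0.78 | 0.59 |
| 60 | 1.02 | 0.85 | 0.71 |

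If Day 84 visits were spread evenly over the window (also assumed), the SD of timing is 28/√12 = 8.08 days. On the log scale this adds 8.08 × ln 2/half-life = 0.28 (20 days) to 0.09 (60 days). Set against the 14-day decline itself, that is 8.08/14 = 58%. Set against between-subject spread it is small: the coefficient of variation of 1.4 in 9.4, read as lognormal, gives a log SD of √ln(1 + 1.4²) = 1.04, and √(1.04² + 0.28²) = 1.08.

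**5. Effect on a model with actual days.** With all four post-dose-3 visits spread evenly in their windows and a log-linear decline, simulation gives a slope variance about 1.03 times that at the nominal days. For the Day 70 to Day 84 segment alone, pooled information is proportional to the mean squared gap. The variance of the gap is (5² - 1)/12 + (29² - 1)/12 = 2 + 70 = 72, so the ratio to a fixed 14-day gap is (14² + 72)/14² = 268/196 = 1.37. Spread sampling times do not lose information when the dates are used.

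**6. What removes the overlap.** The lower limit must be later than Day 72: 84 - 11 = 73 is clear, 84 - 12 = 72 touches. At ± 7 the shortest gap is 77 - 72 = 5 days. At ± 4 it is 80 - 72 = 8 days, and the longest is 88 - 68 = 20.

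**The case against.** The strongest reply is that nothing important rests on this window. No objective or endpoint is a decline from 14 to 28 days after dose 3. Both Mann-Whitney comparisons use Day 70, whose ± 2 window is tight. The duration objective spans eight months and is to be modelled longitudinally. Section 9.1 calls the study exploratory. Whether the model uses actual or nominal days is commonly settled in a statistical analysis plan, so its absence here is no fault. All of this stands.

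The comparison with ± 4 is also open to challenge. Days 28 and 56 are vaccination visits, where the window also controls the dosing interval. Day 84 has the same half-width as the later follow-up visit, "STUDY DAY 140 +/- 14 (84 DAYS AFTER THIRD VACCINATION". That is fair, and it means ± 4 is one option and not a standard the protocol has broken. It does not excuse the overlap: Day 140 ± 14 stays at least 28 days clear of the Day 84 window.

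A reader might infer that the early antibody decline is not reliably measured, or that using actual days cannot make up for it. The documents do not support either reading, as steps 4 and 5 show: the blurring arises when dates are ignored. A reader might also take reversed order as a practical risk. It is possible only by the letter of the windows, since the flow sheet places Day 70 before Day 84.

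What survives is that a stated window lets a visit be compliant at a time that contradicts its own heading.

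**Conclusion.** A real but minor schedule defect. The overlap on Days 70-72 follows from the text alone, as does the range of 14 to 42 nominal days for a visit labelled 28. Neither needs an assumption.

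The consequence is limited to by-visit descriptions of ELISA and of B and T cell responses at Day 84, and to the comparability across subjects of the one autoantibody sample scheduled between Days 63 and 236. The size of the ELISA blurring depends on a half-life that the protocol does not give and on how visits are booked; under the assumed 20 to 60 days it adds at most about 0.28 on the log scale. The Day 70 endpoint is untouched. With actual sampling days the overall decline remains estimable from the four post-dose-3 visits, at a cost of about 3% in slope variance under even spread and log-linear decline.

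**What to change.** In 5.17 and the contents, narrow the Day 84 window so that it cannot meet Day 70 ± 2. Any half-width of 11 days or less does this. A choice such as ± 7 (Days 77-91) or ± 4 (Days 80-88) also leaves a useful interval between the samples. Use actual days since dose 3 as the time variable in the longitudinal model, whichever window is chosen.

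The edit is one line in each place. The cost is that somewhat more visits will be recorded as out of window, and if those count as deviations, Section 1.6 requires each to be reported within 72 hours. That is a reason to choose the widest window that still keeps the two visits usefully apart.

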5.18 STUDY DAY 140 +/- 14 (84 DAYS AFTER THIRD VACCINATION)

1. Perform interim history and perform physical exam if indicated by complaints or history.
2. Obtain blood for hematology, B and T cell analysis, anti-AMA-1 antibody ELISA.

5.19 STUDY DAY 236 +/- 30 (180 DAYS AFTER THIRD VACCINATION)

1. Perform interim history and perform physical exam.
2. Record vital signs.
3. Obtain blood for hematology, rheumatoid factor, anti-dsDNA, ANA, B and T cell analysis, anti-AMA-1 antibody ELISA and GIA.
4. Obtain urine for urine dipstick testing.

5.20 PLASMAPHERESIS

Plasmapheresis will be performed on subjects who develop high levels of AMA-1 antibody and who agree to this procedure. The purpose of plasmapheresis will be to collect serum to serve as an antibody standard for future trials. The criteria for selection as a potential plasmapheresis donor will be the development of a serum AMA-1 antibody level of greater than 2000 AMA-3D7 MVDB ELISA units on Day 42. These subjects will be asked if they would be willing to undergo plasmapheresis, and if agreeable, will sign a separate consent for this procedure. If possible, up to 5 subjects will participate. Participation in the plasmapheresis component of the study does not otherwise impact participation in the main study.

Plasmapheresis will be performed by standard techniques by qualified personnel. The procedure will entail the removal of blood, the separation of 250-500 mL of plasma, and the reinfusion of red blood cells with calcium citrate and electrolytes, as per standard plasmapheresis procedures. Because all red blood cells are re-infused, no blood volume is lost and the total amount of blood drawn during the study remains unchanged.

5.21 MONITORING SUBJECT COMPLIANCE PL

Compliance with the study protocol and protocol mandated study visits will be recorded in the case report form. Subjects who miss study visits will be called and urged to return but will not be dropped from the study once they have already been vaccinated.

5.22 STUDY EVENTS FLOW SHEET

The following table summarizes the events in the study, and estimates the total volumes of blood drawn at each visit and in total.

			V1	V2	V3	V4	V5	V6	V7	V8	V9	V10	V11	V12	V13	V14	V15
	BV*	Pre	0	3	7	14	28	31	35	42	56	59	63	70	84	140	236
Hx and Exam		X															
Informed consent		X															
Interim Hx, Exam			X	X	X	X	X	X	X	X	X	X	X	X	X	X	X
CBC & differential**	5	X	X	X	X	X	X	X	X	X	X	X	X	X	X	X	X
Chemistries	5	X	X	X		X	X	X		X	X	X		X			
Urinalysis		X	X			X	X			X	X			X	X		X
Urine pregnancy***		X	X				X				X						
HIV, HBV, HCV	10	X															
RF, Anti-dsDNA, ANA	5	X	X		X		X		X		X		X		X		X
C3, C4, CH50	5		X														
VACCINATION			X				X				X						
Anti-AMA1 antibody	10		X			X	X			X	X			X	X	X	X
GIA	20		X							X	X			X			X
B cell analysis	20		X	X	X		X	X	X		X	X	X	X	X	X	X
T cell analysis	10		X	X	X		X	X	X		X	X	X	X	X	X	X
Total Blood (mL) drawn		25	80	40	40	20	55	40	40	40	75	40	40	70	50	45	70

* - BV = Blood volume (mL) required for test. Total volume drawn over course of study is 770 mL.

** - CBC parameters to be assessed for safety: WBC, Hemoglobin, Platelet count,

*** - Female subjects only

6 ASSESSMENT OF OUTCOME/IMMUNE RESPONSE

6.1 OUTCOME PARAMETERS

The following parameters will be considered evidence of the efficacy of vaccination in inducing malaria-specific immune responses.

6.1.1 Serum antibody response to vaccination

6.1.2 Cellular immune response to vaccination

6.2 METHODS AND TIMING OF OUTCOME ASSESSMENTS

The following approach will be used to assess these parameters:

6.2.1 Antibody assay (ELISA):

Antibody levels to the AMA-1 antigen will be measured in serum by ELISA. Briefly, microwell plates (Dynex Technologies) are coated overnight at 4°C with 100 µl/well of antigen solution (1 µg/ml). Plates are washed with TRIS-buffered saline(TBS) containing 0.1% Tween-20 (0.1% T-TBS) and blocked with TBS containing 5% skim milk powder for two hours at room temperature. After washing with 0.1% T-TBS, serum samples in TBS containing 5% skim milk are added in triplicate and incubated with AMA-1-coated plates for 2 hours at room temperature. After incubation, unbound antibodies are removed by washing the plates with 0.1% T-TBS, and 100 µl of alkaline phosphatase-conjugated goat anti-human IgG solution (Kirkegaard & Perry Labs, Gaithersburg, MD, 1:1000 dilution in 0.5% T-TBS containing 1% BSA,) is added to each well and incubated for 2 hours at room temperature. Plates are then washed with 0.1% T-TBS, followed by adding 100 µL of substrate solution (Sigma 104 substrate, St. Louis, MO) to each well; the plates are then covered with aluminum foil and incubated for 20 minutes at room temperature for color development. The plates are read immediately at 405 nm with a microplate reader (Spectramax 340PC Molecular Devices). A serially diluted standard serum is run on each plate and will initially be obtained from a pool of human anti-AMA1 serum from malaria-endemic area of Mali. This serum is assigned a unit value as the reciprocal of the dilution giving an O.D. =1 on an AMA1-coated plate. Using the standard curve, the absorbance of individual test sera is converted to antibody units (SOFTmax PRO ver. 3; Molecular Devices Co.).

6.2.2 In vitro Parasite Growth inhibition assay (GIA):

Late trophozoite and schizont stages of *P. falciparum* parasitized erythrocytes are collected by Percoll gradient and/or 5% sorbitol treatment. The synchronized parasites are diluted with human RBCs to give a final concentration of 0.3% parasitemia, 1% hematocrit in growth medium (RPMI 1640 containing 10% human O+ serum, 25mM HEPES, 0.4mM hypoxanthine, 30mM sodium bicarbonate and 25mg/Li of gentamicin). Preliminary tests may be performed with test serum which has been heat inactivated (at 56°C for 20 minutes) and pre-adsorbed with uninfected human O+ RBCs to remove anti-human immunoglobins. However, definitive studies are performed with IgG purified from human serum. Serial dilutions of immune serum or IgG are mixed with parasitized erythrocytes in 96-well tissue culture plates. Controls include autologous pre-immune serum (20%), human AB+serum (+), and uninfected erythrocytes (-). *P. falciparum* cultures are grown in 5% O₂, 5% CO₂, and 90% N₂ at 37°C for 40 hrs. After mixing, 50 µl samples are transferred to C-bottom 96-well plates containing 250 µl of cold PBS. Plates are then centrifuged to pellet the cells and frozen for at least 3hr to lyse the cells. Relative parasitemia levels are determined by means of a colorimetric measurement of parasite lactate dehydrogenase (LDH) activity. Test samples are dissolved in LDH substrate buffer (100uL of 100mM Tris,pH 8.0, containing 50 mM sodium L-lactate, 0.25% TritonX-100, 0.075mM 3-acetylpyridine adenine dinucleotide(APAD), 1U/ml diaphorase, 20 µg Nitro Blue Tetrazolium (all reagents from Sigma Chemical, St. Louis, MO)) and color allowed to develop in the dark for 30 minutes at room temperature. Absorbance at 650 nm is then determined using a Spectra Max 340PC (Molecular Devices) plate reader. Percent growth inhibition is calculated by the formula: $100\% - [(A_{650} \text{ immune sample} - A_{650} \text{ normal RBC only}) / (A_{650} \text{ Pre-immune control} - A_{650} \text{ RBC only})] \times 100\%$. All assays are run in triplicate.

